1. PREVIOUS STUDY HISTORY

Has this study ever been reviewed and rejected/disapproved by another IRB prior to submission to this IRB?

No Yes – if yes, please explain: []

2. BRIEF SUMMARY OF RESEARCH

- *The summary should be written in language intelligible to a moderately educated, non-scientific layperson.*
- *It should contain a clear statement of the rationale and hypothesis of your study, a concise description of the methodology, with an emphasis on what will happen to the subjects, and a discussion of the results.*
- *This section should be no more than ½ page*

This study, sponsored by Nihon Kohden, aims to determine the sensitivity and specificity of synthesized 18-lead electrocardiogram (ECG) in the diagnosis of posterior-lateral and/or right-ventricular ischemia, using actual 18-lead ECG as the gold standard. The synthesized 18-lead ECG calculates six extra leads of information from the standard 12-lead ECG done in the Emergency Department (ED). Nihon Kohden has created synECi18 Technology, which can mathematically synthesize and display the extra leads.

A standard 12-lead ECG records electrical information primarily from the left side of the heart, both anterior and inferior. A 12-lead ECG is commonly performed in the ED to detect abnormal heart rhythms and is the standard of care for patients with chest pain or suspected cardiac ischemic conditions. An 18-lead ECG records the same information as the 12-lead ECG, in addition to six leads that record the electrical information from the right and posterior sides of the heart. 12-lead ECGs are generally considered poor at recording electrical information from the right and posterior sides of the heart.

The patient population (n=300) will consist of patients who present to the North Shore University Hospital or Long Island Jewish Medical Center ED with a chief complaint of chest pain, chest pressure, or chest discomfort. These patients will be receiving a standard 12-lead ECG as part of their routine clinical care. Patients with ST-Elevation Myocardial Infarction (STEMI) will be excluded from the study as they need to be immediately sent to the cardiac catheterization lab and approaching these patients for informed consent to participate in this study would interfere with patient care. Additionally, patients with a known positive troponin value will also be excluded as they also require immediate clinical care.

Trained ED study technicians will use ECG machines provided by Nihon Kohden to obtain two consecutive 15-lead ECGs. The 15-lead ECG consists of a traditional 12-lead ECG and an additional three leads on the right side of the body. The first 15-

lead ECG will have an additional three electrodes/stickers on the right side of the chest and the second 15-lead ECG will have an additional three electrodes/stickers on the posterior side. This means the patient will have a total of six extra electrodes/stickers placed on their body—three on the right side of the chest and three on the back. Each ECG takes about 15 seconds to obtain, of which 10 seconds are recorded by the machine. The two 15-lead ECGs are then saved onto the ECG machine identified by a patient ID number and printed.

The saved information will later be input into an algorithm to calculate the synthesized 18-leads. This will occur towards the end of the study, and the patient will not be involved in this process. In other words, the device will take the actual information from the standard 12-leads and synthesize the six extra leads. The actual 18-leads (composed of the two 15-leads conducted in the ED) will be compared with the synthesized 18-leads produced by the synECi18 technology. A study cardiologist will evaluate the actual 18-lead ECGs and synthesized 18-lead ECGs and determine whether there is posterior-lateral and/or right-sided ventricular ischemia. The cardiologist will be blinded to the type of waveform they are analyzing (synthesized versus actual). There will only be one cardiologist who will evaluate ECGs for this study in a blinded fashion. The actual 18-lead ECGs will be used as the reference for comparison. The synthesized 18-lead ECGs will be compared with the actual 18-lead ECGs to calculate sensitivity and specificity.

The study will not interfere with patient care or treatment, however, the two 15-lead ECGs done in the ED will be shown to the physician who can determine whether or not to order an official 18-lead ECG in the hospital's electronic medical record system.

We hypothesize that the synECi18 synthesized 18-lead ECGs will provide high sensitivity and specificity for diagnosing posterior-lateral and/or right-ventricular ischemia, with the actual 18-lead ECGs being used as the reference for comparison.

3. RESOURCES AVAILABLE TO CONDUCT THE HUMAN RESEARCH

- *Explain the feasibility of meeting recruitment goals of this project and demonstrate a potential for recruiting the required number of suitable subjects within the agreed recruitment period*
 - *How many potential subjects do you have access to?*
- *Describe your process to ensure that all persons assisting with the trial are adequately informed about the protocol and their trial related duties and functions*

In 2016, there was an average of 686 patients per month who presented to the Long Island Jewish Medical Center (LIJMC) ED and the North Shore University Hospital (NSUH) ED combined with a chief complaint of chest pain. Conservatively estimating that 10% of these patients would not be eligible due to out exclusion criteria, there will be approximately 618 eligible patients per month. Given that we will be obtaining a convenience sample (i.e. between the hours of

9am and 5pm when study ED technicians are available), we are allowing 6 months to enroll 300 patients.

All Academic Associates and study ED technicians participating in this study will be trained by Nihon Kohden representatives on how to operate the ECG machines provided by Nihon Kohden.

4. RECRUITMENT METHODS

- *Describe the source of potential subjects*
- *Describe the methods that will be used to identify potential subjects*
- *Describe any materials that will be used to recruit subjects. A copy of any advertisements (flyers, radio scripts, etc.) should be submitted along with the protocol.*
- *If monetary compensation is to be offered, this should be indicated in the protocol*

Academic Associates, full-time research assistants in the emergency department, will screen the ED status board for patients with a chief complaint of chest pain, chest discomfort, or chest pressure and will use the triage note and a conversation with the attending physician to determine if the patient qualifies for the study. If the patient qualifies, the Academic Associate will explain the study to the patient and, if interested, obtain informed consent from the patient to participate in the study.

Once informed consent is obtained, the Academic Associate will inform a trained study ED technician that the patient has been enrolled in the study. At a time that is convenient for the ED technician and that does not interfere with the patient's care, the ED technician will perform two consecutive 15-lead ECGs on the study patient and fill out the patient entry form (see attached).

Inclusion criteria:

- Subjects with a chief complaint of chest pain or chest discomfort or chest pressure
- Troponin test has been ordered (unknown positive at time of recruitment)
- Subjects are capable of providing informed consent
- English speaking

Exclusion criteria:

- STEMI patients
- Patients who have not had a troponin test ordered
- Pregnant women
- Patients under 18 years of age
- Prisoners

STEMI patients will be excluded from this study, as STEMI patients require immediate intervention. Approaching STEMI patients for participation in this study would interfere with clinical care.

Pregnant women will be excluded from this study because it would be uncomfortable to ask pregnant women to turn on their sides or back in order to place the additional electrodes/stickers on the right side of their chest and back.

Prisoners will be excluded because correction/police officers will be with them. Approaching prisoners for participation would interfere with correction/police officers as they do their job.

5. NUMBER OF SUBJECTS

- *Indicate the total number of subjects to be accrued locally. If applicable, distinguish between the number of subjects who are expected to be pre-screened, enrolled (consent obtained), randomized and complete the research procedures.*

The first phase of the study will be a pilot study, which will consist of enrolling 10 subjects to pilot test our data collection procedures and operations outlined in this protocol, as well as to troubleshoot issues that we did not expect. After our data collection procedures and operations are pilot-tested, the study will move onto the next phase for data collection.

The pilot study phase may take approximately two weeks to enroll 10 subjects. The main phase of the study will be the data collection phase, which is estimated to take 6 months. The data collection phase will consist of enrolling the remaining 290 subjects in the ED at NSUH or LIJMC.

6. STUDY TIMELINES

- *Describe the duration of an individual's participation in the study*
- *Describe the duration anticipated to enroll all study subjects*
- *The estimated date of study completion*

The study will require obtaining two 15-lead ECGs on all enrolled patients. Each ECG takes approximately 30-seconds to complete. Placing the additional six electrodes/stickers on the patients will take less than five minutes. This means that the study ECG procedures should only take less than approximately 8 minutes. The consent process length will depend on the questions the patient has about the study. As stated, the patient will be left with the consent form for about 10 minutes to read it over in private. Taking into account this time, the consent time, and the study itself, we expect each patient enrollment will take 25 to 30 minutes.

The full study is expected to last approximately 9 months and will consist of three total phases. The first phase will be a pilot study conducted on 10 subjects to pilot test our procedures and operations of data collection outlined in the protocol. After we pilot test our procedures and operations, the study will move onto the data collection phase. This pilot study phase, which requires enrolling 10 subjects, will take approximately two weeks.

The main phase of the data collection period is expected to take about 6 months. This phase requires the enrollment of 290 subjects at NSUH ED and LIJMC ED. It is estimated that target patient enrollment could be 5 subjects per day per hospital, allowing the study to collect 50 patient ECG data sets per week. It is expected that data collection may be complete sooner than 6 months, however, some delays are taken into consideration. The study will begin at NSUH ED and once it is running well there, it will begin at LIJMC ED.

The evaluation phase of the study is expected to take 3 months. This phase will consist of analyzing all of the data.

Table of timeline:

Pilot Study Phase (Month 1)	Main Data Collection Phase (Months 2-6)	Evaluation Phase (Months 7-9)

 • Pilot trial with up to 10 subjects 	
 • Subject enrollment (290 subjects) • Data collection 	
 • ECG analysis • Data report

7. RESEARCH PROCEDURES

- *Provide a description of any procedures that differ from what is described in the main study protocol.*

- 1) Identification: Patients will be screened for the study upon arrival to the ED by an Academic Associate (AA) who will be scanning the ED status board on Sunrise. The patients will be identified via chief complaint and triage notes as well as results to confirm there is no positive troponin result. The AA will speak to the physician and then the patient to determine if the patient is eligible for the study. This will be tracked through a screening log to ensure patients are not approached twice (screening log attached). Information on the screening log will be entered into REDCap at the end of the day, and the paper screening log will be destroyed.
- 2) If the patient is eligible, the AA will explain the study and consent form to the patient. The AA will also answer any questions the patient may have regarding the study.
- 3) The AA will allow the patient 5-10 minutes to review the consent form in private.
- 4) The AA will allow time for the patient to ask any new questions regarding the study or the consent form.
- 5) If the patient is interested in continuing with the study, the AA will obtain informed consent.

- 6) The AA will inform a study ED technician that a patient has been enrolled as well as the patient's location.
- 7) At a time that is convenient for the ED technician and that does not interfere with patient care, the ED technician will complete the patient entry form and obtain two consecutive 15-lead ECGs using the Nihon Kohden 15-lead ECG study machine. Only the patient ID will be entered into the machine. The patient will only be identified by their MRN on the patient entry form, which will be stored in a locked cabinet in the AA office. No identifiers will be stored in the study ECG machine. The AA will be with the ED technician when the 15-lead ECGs are being performed, to collect the patient entry form.
- 8) The two 15-lead ECGs will be printed out and shown to the physician. Then, the printed ECGs will be saved in the AA office in a locked cabinet identified only by the subject ID. The ECG results will not be used directly for any clinical decision making. The physician will decide if they would like to order an official 18-lead ECG after seeing the printed results from the study. The study ECGs will not be used for any clinical decisions.
- 9) Following the patient's ED visit, an AA will use the MRN and the ECG date from the data entry form to obtain test results for the patient obtained during their ED stay. These include troponin test, CAGs, CTA, stress echos, or nuclear stress tests. This data will be entered directly into the REDCap database (see attachment 2). Only IRB approved study personnel will have access to this database. At the end of the study, NKC, the sponsor, will be provided with the de-identified version of the data sheet (i.e. all points included in attachment 2 except the MRN).
- 10) All ECGs (synthesized and actual) in this study will be assigned a random code by the Academic Associate on this study, [name], and only she will have access to this code. The ECGs will be coded randomly with numbers provided by the randomization tool in Excel. The file with the random codes will be saved onto Northwell Health servers and a password will be placed on that document. Once coded, the ECGs will be put in numerical order to avoid ECGs from the same patient being back to back. The study cardiologist will analyze the ECGs in that numerical order and determine whether or not the ECG shows evidence of ischemia. This coding will shuffle the ECGs from all patients and all dates. The study cardiologist will not know which ECGs are synthesized vs. actual. The study cardiologist will record the random code on the ECG and their interpretation for that ECG on a form (form attached). The form will be provided to the Academic Associate, who will decode the ECG and enter the data into REDCap. Given that there will only be one study cardiologist, there will be no need to evaluate inter-rater reliability.
- 11)

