enroll 300 patients; therefore, we estimate that 30 of these patients will have our outcome of interest and 270 will not. Based on a previous study by Tamura et al. published in the American Journal of Cardiology in 2014, sensitivity is estimated to be 83% and specificity is estimated to be 99%. Therefore, among the 30 patients with our outcome, the proportion of test positive by the synthesized 18-lead ECGs is estimated to be 83% with a corresponding 95% CI of 65% to 94%. Among the 270 patients without our outcome, the proportion of test negative by the synthesized 18-lead ECG is estimated to be 99% with a corresponding 95% CI of 97% to 100%.

No formal sample size calculations were performed for this study. Data collected from this study will allow us to perform a formal sample size calculation for future studies.

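### Sorting by an unrestricted random code does not ensure that a patient's two tracings are kept apart; the effect is small, and a two-block reading order fixes it cheaply

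*Combined protocol and SAP*

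**What the plan says.** Section 7 (Research Procedures), step 10, describes the reading order. Synthesized and actual tracings are pooled, and "The ECGs will be coded randomly with numbers provided by the randomization tool in Excel". The purpose of the sort is stated: "Once coded, the ECGs will be put in numerical order to avoid ECGs from the same patient being back to back". The cardiologist then reads in code order without knowing the tracing type. Only the coder has access to the codes, and the shuffle runs over all patients and dates. The step mentions no reading blocks, minimum spacing, pause or check of the resulting order.

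Section 2 (Brief Summary of Research) adds two facts that bear on this. There is a single reader: "There will only be one cardiologist who will evaluate ECGs for this study in a blinded fashion". The two tracings of a patient also share their source, because "the device will take the actual information from the standard 12-leads and synthesize the six extra leads".

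**The concern.** The same person makes the reference call and the index call for every patient, and the synthesized leads are computed from that patient's own standard 12-lead data. If the reader recognises a tracing, the second call will tend to follow the first. That error has a direction: it moves discordant pairs toward agreement and so raises both sensitivity and specificity.

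The plan itself treats back-to-back reading as something to prevent, but the method it names leaves that to chance. It matters before reading starts, because the order cannot be repaired once the only reader has seen the tracings.

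**Working it through.** **Inputs.** Section 8 (Statistical Analysis) gives 300 patients, 30 with and 270 without the outcome, sensitivity 83% (95% CI 65% to 94%) and specificity 99% (97% to 100%). Section 2 implies one actual and one synthesized 18-lead per patient: "The actual 18-leads (composed of the two 15-leads conducted in the ED) will be compared with the synthesized 18-leads produced by the synECi18 technology". Two tracings per patient, hence 600 reads, is an assumption. It is the natural reading of the 2x2 table, but the number of items handed to the reader is not stated.

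**1. The plan's own figures.** Exact (Clopper-Pearson) intervals are 65.3% to 94.4% for 25/30 and 96.8% to 99.8% for 267/270. Both stated intervals are reproduced. The plan gives no figure for adjacency.

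**2. Expected adjacent pairs.** In a random order of 600, a given pair is adjacent with probability 2/600. Expected number = 300 × 2/600 = 1.0. Among the 30 positives it is 30 × 2/600 = 0.1.

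**3. Chance of at least one.** By inclusion-exclusion, P(none) = Σ (−1)^k C(300,k) 2^k (600−k)!/600! = 0.3676, so P(at least one) = 63.2%. A simulation of 20,000 orders gave 63.0%, with two or more in about 26%. If the 10 pilot patients are left out (290 patients), both results are unchanged.

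**4. Near neighbours.** P(gap ≤ k) = Σ_{d=1..k} (600−d)/C(600,2).

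| Within k positions | P per patient | Expected pairs of 300 |
|---|---|---|
| 1 | 0.0033 | 1.0 |
| 10 | 0.0331 | 9.9 |
| 20 | 0.0656 | 19.7 |

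The median gap is 176.

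**5. Effect on the estimates.** Suppose every pair within k positions is forced to agree. Discordance is 100 − 83 = 17 points among positives and 100 − 99 = 1 point among negatives, so the expected shifts are 17 × P and 1 × P.

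- k = 1: sensitivity 17 × 0.0033 = 0.06 points.
- k = 10: sensitivity 17 × 0.0331 = 0.56 points.
- k = 20: sensitivity 17 × 0.0656 = 1.1 points; specificity 1 × 0.0656 = 0.07 points.

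The interval for sensitivity spans 94 − 65 = 29 points. This calculation lets the synthesized call move. If the actual tracing is read second, the reference call moves instead, and the direction is the same: one missed positive turned into agreement gives 26/30 = 86.7% in the first case and 25/29 = 86.2% in the second, from 25/30 = 83.3%.

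**6. More tracings per patient.** With m tracings per patient, each of the (300m − 1) neighbouring positions holds the same patient with probability (m − 1)/(300m − 1), so m − 1 adjacencies are expected: 1, 2 and 3 for m = 2, 3 and 4. Any departure from the two-tracing assumption in that direction makes the problem larger.

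**7. Two blocks of 300, shuffled separately, no pause.** Expected pairs within k = 300 × [k(k+1)/2]/300².

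| Within k positions | Plain sort | Two blocks |
|---|---|---|
| 1 | 1.0 | 0.0033 |
| 10 | 9.9 | 0.18 |
| 20 | 19.7 | 0.70 |

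The chance of an adjacent pair is 1/300 = 0.33%, and the simulated median gap is 300.

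**8. Re-drawing instead.** Discarding orders with any adjacent pair takes 1/0.3676 = 2.7 draws on average. Wider spacing is not practical this way. In separate runs of 20,000 plain orders, every patient's gap exceeded 5 in only 0.5% to 0.8% of orders, and exceeded 10 in at most one order.

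**The case against.** The plan says the sort is meant to avoid adjacency; it does not promise to exclude it. Against reading in patient order, where all 300 pairs could be adjacent, leaving about one is avoidance in the ordinary sense: about 299/300 = 99.7% of patients are separated. Type blinding, restricted access to the codes and the shuffle across patients and dates already limit recall. The 1.1-point figure requires the reader to copy the earlier call in every pair within 20 positions, a rate the documents do not support. No pass/fail threshold is set, and the data are meant to inform a later sample size calculation, so no conclusion would turn on a shift this small.

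Most of this stands, and it is why the point is minor. It does not remove the gap between the stated purpose and the method: adjacency somewhere in the list is more likely than not.

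Two further objections have substance. Two blocks without a pause are not perfect either: the median smallest gap over all patients is about 20 positions, and about 52% of simulated orders still had some pair within 20. The pause and a check at the block boundary are therefore part of the remedy. Nor do the documents give a reading time, so the room for a pause in the evaluation phase cannot be verified exactly.

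**Conclusion.** The concern holds, as a minor one. The ordering rule does not secure the separation it is meant to provide. The documents do not show how often recall would occur, and the finding does not imply that the reads are unprotected: most pairs are far apart and the reader is blinded to type. Even under full carry-over the expected inflation of sensitivity runs from 0.06 points (adjacent pairs only) to about 1.1 points (within 20 positions), well inside the plan's own uncertainty. These figures rest on 600 reads in one random sequence and on the plan's 83% and 99%. The case for acting is that the possible bias has a known direction and prevention costs very little.

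**What to change.** Replace the single sort in section 7, step 10, with restricted randomization. Suggested text:

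> For each patient, one tracing (actual or synthesized, chosen at random and balanced 150/150) is placed in reading block 1 and the other in block 2. Each block is shuffled separately. If the last tracing of block 1 and the first of block 2 belong to the same patient, block 2 is re-shuffled. Block 2 is read after a pause fixed before reading starts.

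Randomizing the type between blocks keeps type from being confounded with reading order. The study team sets the length of the pause. The step should also state how many items per patient the reader receives. At a minimum, re-draw the codes until no same-patient pair is adjacent.

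The cost is a slightly more complex coding sheet and the pause. The number of reads is unchanged. Synthesis is done toward the end of the study, so all tracings can be coded before reading begins. Section 6 (Study Timelines) states "The evaluation phase of the study is expected to take 3 months"; the pause should be chosen to fit within that period alongside the data report.
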